Study-wide data management:

- **Data Access:** Only authorized personnel listed on each institution's IRB will have access to the data.
- **Data Storage:** The research staff will collect data through the Northwestern RedCap survey platform. Data will be stored in REDCap, a secure, web-based application, and on the Northwestern secure servers for the length of the study. The PI or Data Analyst will download the data from REDCap monthly and save to the "Analytic" folder within the project folder on the FSM department servers which are located in a HIPAA compliant data center. These downloaded data files do not contain any identifiable information, and are identified by project staff by an assigned study ID. Upon completion of all study activities, a final de-identified dataset will be created. This dataset will be stored indefinitely on the GIM server for secondary analyses. Only authorized personnel will have access to the dataset. All identifiable information will be deleted upon completion of the study.

PROVISIONS TO MONITOR THE DATA TO ENSURE THE SAFETY OF PARTICIPANTS

Data Safety and Monitoring Board (DSMB). The Scientific Advisory Board will serve as a mini DSMB. This group will be formed early in the project and be given responsibility to review and approve the methods and analysis plan. It will be organized by [name] and include an epidemiologist, and two clinical or health services researchers with related expertise. Meetings

STU#: STU00217596

will be held via video-conference at least annually to review protocols, procedures, and concerns related to research integrity.

PROVISIONS TO PROTECT THE PRIVACY INTERESTS OF PARTICIPANTS

Information about study subjects will be kept confidential and managed according to the requirements of the Health Insurance Portability and Accountability Act of 1996 (HIPAA). All study generated datasets will be stored on the FSM server. In order to preserve participants' confidentiality rights, research subjects will be assigned code numbers that will be used to identify all the information collected. Using these codes, none of the collection forms will contain the names of the participants. All electronic data will be stored in on a password-protected computer. A master study tracking database will be created using REDCap and will be kept separate from all study responses that are also collected in REDCap. This database will be kept on a secure server and only accessible by study personnel. Survey data will also be stored in a REDCap. Audio recordings from qualitative interviews will be saved directly into a file on the FSM server from the web conferencing software; these will be sent for transcription. Deidentified transcripts will be kept used for analyses; audio recordings will be deleted at the end of the study. EHR extraction data will be stored on the FSM server. The data will not contain any identifiable information. Individual study identification numbers will be assigned to each participant. The master study tracking REDCap project will include consent data, which includes the participants' name and date of births, and an email to be able to send the electronic consent. REDCap has protections needed for storage of PHI and will restrict data downloads to exclude PHI. These links will be removed after completion of data collection. The REDCap project will only be accessible to authorized study personnel. All personnel involved in data collection will be thoroughly trained. Only information that has been generalized and/or de-identified will be shared.

Subjects will be informed that participation in any part of this research study may result in a loss of privacy, since persons other than the investigators may view their study records if deemed necessary for oversight purposes. However; they will be identified by a unique identification number ("study id"), not by name, and any other identifying information (e.g. personal and/or contact information) will be kept separate from the other data; all information will be kept in secure, password-protected files. Personal information will be encrypted and linked to the study number. Further, subjects will be told that unless required by law, only the study investigators, members of the project staff, and representatives of the Northwestern University and local Institutional Review Boards will have the authority to review any study records. In such case, they too will be required to maintain confidentiality.

Participation in the study poses minimal risk of psychological, social, and economic harm. Informing subjects in advance that they may decline to answer any questions asked during the interview and discussion group will mitigate any risks associated with expressing their opinions (e.g., feeling uncomfortable).

All enrolled participants in Aim 1 will provide online consent. All enrolled participants in Aim 2 will provide electronic consent through REDCap.

COMPENSATION FOR RESEARCH-RELATED INJURY

NA

ECONOMIC BURDEN TO PARTICIPANTS

NA

CONSENT PROCESS

STU#: STU00217596

Aim 1 Participants. The Northwestern study team will screen all patients to ensure they meet the study's eligibility criteria. Participants who are recruited for Aim 1 (cognitive interviews) will undergo informed online consent.

After initial recruitment and screening by phone, subjects will be informed about the nature of the study by a trained RC and asked to provide online consent. Participants will be provided a consent form. Informed consent will be viewed as a process, i.e. at several times during review of the IRB approved consent document, the subject will be asked to explain in their own words what their understanding of the consent. This will enable the research personnel to enter into a dialogue with the subject and ensure that the subject understands that he/she is free to withdraw at any time without penalty. Information will be provided to the subjects in terms that they can fully understand. They will be informed that they may withdraw from the study at any time and given contact information for the PI and RC. There will be no exertion of any overt or covert coercion. They will be encouraged to ask questions prior to giving consent.

If a patient agrees to participate after the RC reads the consent, the RC will digitally sign their own name on the form using REDCap. This signed consent form will be saved on a secure FSM server, in a project folder only accessible by IRB approved personnel. Subjects will also be mailed or emailed the consent forms to keep for their records.

Aim 2 Participants. Patient participants who are recruited for participation in the post-pilot interviews (Aim 2) will provide electronic consent with HIPPA authorization. Prior to the post-pilot interview, participants will electronically provide consent. Similar to the consent process for Aim 1, the RC will send patients a link to REDCap by email to be able to read through the consent with the RC. Informed consent will be viewed as a process, i.e. at several times during review of the IRB approved consent document, the subject will be asked to explain in his/her own words what his/her understanding of the consent. This will enable the research personnel to enter into a dialogue with the subject and ensure that the subject understands that he/she is free to withdraw at any time without penalty. Information will be provided to the participants in terms that they can fully understand. There will be no exertion of any overt or covert coercion. They will be encouraged to ask questions prior to giving consent. Participants will be informed about the nature of the study by a CITI certified RC and asked to provide consent. Additionally they will be notified that only those contents of their medical record that are necessary to evaluate the effectiveness of the intervention will be released to the research team at Northwestern. They will be informed that they may withdraw from the study and stop the interview at any time; they will be given contact information for the PI and study coordinator. The patient will then complete an electronic consent and HIPAA Authorization through REDCap. Patients will be informed they can print their screen to keep a copy of the consent, or we can mail or email them a blank copy of the consent document for their records. Prior to completing the phone interview, the RC will review the electronic consent with the patient and confirms the consent was properly signed and completed.

Non-consenting patients. Participants in the post-pilot interviews (Aim 2) are consenting to post-pilot interviews; however, because of the nature of implementing the EMC² PrEP intervention other eligible patients will receive the EHR components of the intervention without being approached for consent or enrolled in the study (this is similar to a quality improvement activity). Patients will receive educational materials via their EHR portal about PrEP and HIV prevention. For these patients receiving the intervention, but not approached or consented for post-pilot interviews, we request a waiver of informed consent because: 1) this is a low-risk study, in particular, it is research designed to evaluate an educational strategy, 2) it would not be feasible to conduct the study as intended if obtaining individual informed consent were necessary, 3) informed consent from each participant would threaten the scientific validity of the study (in this

STU#: STU00217596

case it would be impossible to evaluate real-world dissemination and implementation of the intervention) and 4) for the patients receiving the intervention, but not completing follow-up, no patient data are collected that would not be routinely collected in usual care without consent. This specific strategy of “turning on” an EHR intervention has been previously approved by the IRB at Northwestern University.

NON-ENGLISH SPEAKING PARTICIPANTS

NA

WAIVER OR ALTERATION OF CONSENT PROCESS

Waiver of HIPAA Authorization are requested to identify subjects (patients) prior to enrollment into the study.

A waiver of consent for eligible patients to receive intervention materials (the PrEP decision guide) is requested. Education materials will be offered as an option for all patients to see and respond to on their own accord, regardless if they consent to the study or not as this will be the clinic standard of care. Materials will inform patients about PrEP, a service that is already offered at the clinic. Because PrEP is most useful to individuals who face an increased vulnerability to HIV, it is prudent to target materials to individuals who have a clinical indication of vulnerability due to recent STI testing and/or diagnoses. Furthermore, targeting as opposed to sending the material to all patients, will help to not overwhelm the practice, should the materials create increased interest in PrEP.

PROTECTED HEALTH INFORMATION (PHI AND HIPAA)

This study involves the use of Protected Personal Health Information for Aim 2 participants. All enrolled participants in Aim 2 will provide electronic consent with HIPAA authorization for the collection of all data, including review of the patient's medical record.

Waiver of HIPAA Authorization are requested to identify subjects (patients in Aims 1 and 2) prior to enrollment into the study. The following will be collected for eligible patients

- Names
- Street address, city, county, ZIP code
- Date of Birth
- Telephone numbers (home, cell, work)
- Email
- Medical Record Numbers
- HIV testing results
- Sexually Transmitted Testing and/or Illnesses

QUALIFICATIONS TO CONDUCT RESEARCH AND RESOURCES AVAILABLE

The research team is comprised of 5 PhD and/or MD level researchers, and 1 research coordinator (with experience on similar projects). [name] (PI) will manage the team, which includes experts in health literacy ([name], [name]), primary care ([name]; [name]), infectious disease ([name]), HIV prevention and PrEP ([name], [name], [name], [name]) and health information technology ([name], [name]).

MULTI-SITE OR COLLABORATIVE RESEARCH:

STU#: STU00217596

NA

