Primary outcomes include process outcomes. The primary outcome of interest is PrEP uptake. Rates of PrEP uptake will be compared in the first 6 months between those in the intervention and control arms; a sensitivity analysis will be conducted to examine de-identified rates of PrEP uptake among others during the same timeframe. Other process outcomes of interest will investigate the reliability of the strategy to 1) deliver an educational PrEP decision

STU#: STU00217596

guide to women with increased vulnerability to HIV, 2) engage those individuals in the PrEP decision guide, and 3) schedule patients for a dedicated PrEP visit

Secondary outcomes include psychosocial outcomes. In post-pilot interviews, we will obtain the following measures. Differences between intervention and control groups will be explored.

The main secondary outcome is PrEP knowledge measured about 2-6 weeks after randomization to the intervention (receiving the materials) or the control (delayed receipt).

Perceived Risk of HIV. We will use the 8-item Perceived Risk of HIV scale to assess how vulnerable an individual feels to HIV. The scale was developed in the United States and attention was paid to health literacy. Response options vary for each item, though they are measured on a 4-point Likert scale.

PrEP Knowledge. We will use a scale created by our team, drawing from the scale previously created by Welsh for use with men.

PrEP Attitudes. PrEP attitudes will be assessed using a recently developed scale developed that includes 5 items, each measured on a 5-point Likert scale (1=strongly disagree to 5=strongly agree).

[figure not shown]
Health Literacy. We will assess health literacy skills via the Newest Vital Sign (NVS).

Participants will be asked to view a nutrition label and to answer 6 questions about how they would interpret the information. Scores are classified as high likelihood of limited literacy (0-1), possibility of limited literacy (2-3), and adequate literacy (4-6). The NVS has a high correlation with the Test of Functional Health Literacy in Adults and includes both reading and numeracy items.

Health Activation. Patients' engagement in their child's healthcare will be measured using a modified version of our team's 10-item Consumer Health Activation Index (CHAI). Response options are a Likert scale; linear transformation is used to put total scores onto a 0-100 scale, with higher numbers indicating greater activation.

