Procedures for post-pilot interviews (N=200). To further explore intervention effects, the study RC will interview 200 participants approximately 2-6 weeks after they have received the materials or after they have been randomized to the control arm. This includes interviewing 100 participants randomized to the EMC² PrEP strategy intervention arm and 100 randomized to the control arm (delayed invitation).

These patients will participate in an interview lasting ~1 hour. This interview will take place either in person, over the phone, or via a secure videoconferencing platform, depending on patient preferences and the status of the COVID-19 pandemic. However, the last 50 intervention arm participants will have their interviews conducted over a secure videoconferencing platform so that the RA can show them the EMC² PrEP education materials (the PDF and the video) before initiating the interview questions. Cameras will be turned off and there will be no recording. The purpose is just to ensure these participants have had a chance to view the materials before they answer study interview questions. All questions will be verbally asked by the RA as if the participant were on the phone and data will be captured in REDCap per usual. Interviews with both intervention arm (N=100) and control arm (N=100) patients will include quantitative measures assessing perceived risk of HIV, as well as PrEP knowledge, attitudes, stigma, and information sources. Additionally, we will measure health literacy, health activation, and basic demographic information.

Patients enrolled in the intervention arm (N=100) will also complete measures of satisfaction, specific to each strategy component.

Aim 3: Dissemination activities (Months 20-22)

These activities will be the last to occur. First, to obtain feedback from clinicians at a participating NM primary care practice(s), we will speak with clinic staff during an available business meeting after the completion of the pilot study to gauge their reactions to the approach. We will specifically aim to identify clinic-level barriers to implementation of the EMC² PrEP strategy.

The Northwestern research team will then solicit opinions about how best to implement this type of study at AllianceChicago affiliated clinics. To achieve this the research team will speak with current clinic administrators, prescribing providers, or EHR analysts within FQHCs affiliated with AllianceChicago or AllianceChicago itself (N~15).

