- 7) have no severe, uncorrectable visual, hearing or cognitive impairments that would preclude study consent or participation.

For the pilot study (**Aim 2**), we will randomize women who are potentially eligible for PrEP (N~1400; n=700 per arm) to intervention (the EMC² PrEP strategy) and control arms (delayed receipt of PrEP education materials). This is similar to a quality improvement activity. To be eligible to receive the EMC² PrEP strategy, participants must:

- 1) be an adult cisgender woman (age 18+) identified in the EHR who:
- 2) be HIV negative,
- 3) have received two or more tests in the past 12 months for chlamydia, gonorrhea and/or syphilis,
- 4) and/or have received a positive diagnosis for at least one of those sexually transmitted diseases (STIs) in the past 6 months;
- 5) are seen at the participating Northwestern Medicine practice(s);
- 6) have an active MyChart account;
- 7) not be currently using PrEP;
- 8) did not participate in the Aim1 cognitive interviews.

To be enrolled in post-pilot interviews (**Aim 2, N=200; n=100 per arm**), women must additionally (in addition to pilot study eligibility criteria):

STU#: STU00217596

- 1) speak English as their primary language; and
- 2) have no severe, uncorrectable visual, hearing or cognitive impairments that would preclude study consent or participation.
- 3) The last 50 intervention arm participants will also need to have access to videoconferencing platform (e.g. Zoom) so that they may view the PrEP education materials (the PDF and the video) before answering the interview questions.

For dissemination activities* (**Aim 3**), we will consult with key informants affiliated with AllianceChicago to explore study expansion. Participants in these consultations will be:

- 1) current clinicians and/or clinic staff from the participating NM site(s)
- 2) current clinic administrators, prescribing providers, or EHR analysts within an FQHC partnering with AllianceChicago or AllianceChicago itself

*Aim 3 Dissemination Activities are not considered human subjects research as these individuals are only providing information that will improve the intervention and/or inform the development of a standard operating protocol; no information will be collected about the participants themselves.

VULNERABLE POPULATIONS

We will not include any vulnerable populations in this research.

PARTICIPANT POPULATION(S)

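### The Health Activation measure is defined as engagement in a child's healthcare, although participants are adult women deciding about their own HIV prevention

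*Combined protocol and SAP*

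**What the plan says.** STUDY ENDPOINTS opens its second group of measures with "Secondary outcomes include psychosocial outcomes" and adds, for the measures that follow, "Differences between intervention and control groups will be explored". Health Activation is one of them. Its entry says that patients' "engagement in their child's healthcare will be measured using a modified version" of "our team's 10-item Consumer Health Activation Index (CHAI"). On scoring it says "linear transformation is used to put total scores onto a 0-100 scale, with higher numbers indicating greater activation". It does not say what the modification was.

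Under PROCEDURES INVOLVED, the description of the post-pilot interviews covers both arms, 100 women in each, and says "we will measure health literacy, health activation, and basic demographic information". No child is mentioned there.

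The pilot criteria under INCLUSION AND EXCLUSION CRITERIA begin with the requirement to "be an adult cisgender woman (age 18+) identified in the EHR who" meets the HIV, STI-testing and other conditions. Neither these criteria nor the extra criteria for the interviews mention being a parent.

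**The concern.** The definition names a construct that does not belong to this trial. A woman's engagement in a child's care is not the same as her engagement in her own care, and only the second bears on whether she takes up HIV prevention for herself. A woman without a child has no meaningful answer to items about a child's care.

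The sentence stands in the endpoint definitions and is the only definition of the measure in the documents. Someone building or checking the interview form from the protocol would have nothing else to work from. Because the index is described as modified without saying how, a later reader could not tell which wording lay behind a reported 0-100 score. At stake is whether one listed secondary measure can be interpreted, both as a description of the sample and in the exploratory comparison of arms.

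**Working it through.** No arithmetic on power or effect size applies: the documents give no such figure for health activation. The check is a comparison of sections.

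1. **Construct as written.** STUDY ENDPOINTS, Health Activation: engagement in the child's healthcare. The sentence is complete and is current text, with no redaction or broken table in it.
2. **Population.** INCLUSION AND EXCLUSION CRITERIA, Aim 2: adult cisgender women, HIV negative, with recent STI tests and/or a recent diagnosis, not using PrEP. There is no criterion about children. The extra interview criteria concern language, impairments and, for the last 50 intervention participants, access to videoconferencing.
3. **Decision under study.** OBJECTIVES, Aims 1 and 2: the woman's own decision about PrEP. Steps 1 and 3 do not fit together.
4. **Any correction elsewhere.** The interview procedures name health activation without defining it. The demographic list under STUDY ENDPOINTS does not name parenthood, although it is stated not to be exhaustive. No section redefines the measure or explains why a child's care would be of interest.
5. **How many interviews could be affected.** 100 intervention + 100 control = 200. This is an upper limit, reached only if every interview used child-worded items. WITHDRAWAL OF PARTICIPANTS says that interviews take place at a single time point, so no later planned contact would recover the measure.
6. **Which outcomes depend on it.** STUDY ENDPOINTS names PrEP uptake as the primary outcome of interest and then says "The main secondary outcome is PrEP knowledge measured about 2-6 weeks after randomization". Quantitative Methods lists PrEP knowledge and uptake together as primary. Under either labelling, neither is computed from the activation index.

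Two cases remain, and the documents cannot separate them:

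| Interview form | Consequence |
|---|---|
| Follows the protocol wording | Wrong construct in up to 200 interviews; no meaningful answer from women without children |
| Already asks about the woman's own care | Data sound; the protocol misdescribes the measure |

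**The case against.** The strongest reply is that this is a stray phrase, perhaps carried over from another protocol. Children appear nowhere else as a subject of measurement, the interview procedures speak only of health activation, and the aims concern the woman herself. That reading is plausible, but the documents do not confirm it. Even if it is right, the sole definition of the measure still needs correcting.

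The reply does limit what can be claimed. A reader might infer more in four ways, and the documents support none of them:

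- *That all 200 interviews measured the wrong thing.* The form is not in the documents and the modification is not described, so this holds only if the form follows the text.
- *That a particular number of scores would be missing or arbitrary.* No figure on parenthood is given, so any count would only be a guessed proportion multiplied by 200.
- *That a planned adjustment is spoiled.* Quantitative Methods names study arm as the primary covariate and leaves the other patient factors unspecified. No section plans to adjust for health activation. The sentence about exploring arm differences introduces a list that also holds health literacy, demographics, and satisfaction asked only of the intervention arm, so it does not establish a specific test for each entry.
- *That the team should return to an unmodified adult form.* The documents describe no such form, and the modification may have a purpose unrelated to children.

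Nothing suggests that the team chose child-focused activation on purpose. This is an error of definition, not a disputed choice of design.

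**Conclusion.** The point holds as an error in the text. The Health Activation definition is wrong as written for this population and this question, and nothing elsewhere puts it right. The effect on the data is conditional: up to 200 uninterpretable activation scores if the fielded items ask about a child, none if they ask about the woman. Whether the form repeats the protocol wording is the one fact on which the size depends, and the study team can settle it by looking.

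The measure is secondary and its comparison between arms is exploratory. Conclusions on PrEP uptake and PrEP knowledge do not change in either case. The severity is minor: a correction worth making, not a threat to the trial.

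**What to change.** In the Health Activation entry under STUDY ENDPOINTS, replace the reference to the child's healthcare with the woman's own healthcare. Add a sentence saying what was modified in the 10-item index and why. Compare the REDCap interview form with the corrected text and record that its items ask about the woman's own care.

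If any completed interviews used child-worded items, document which ones and do not report those scores as the woman's own health activation.

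The cost is one changed phrase, one added sentence and a check of the form. Sample size, the interview schedule and the main analyses stay as they are.
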